ISIS 678354 was well-tolerated, there was low incidence of predominantly mild injection site reactions (12.2% vs. 4.2%), and flu-like reactions (8.9% vs. 8.3%) in patients treated with ISIS 678354 compared to placebo, respectively.

No dose- or time-dependent changes in platelet count were observed, and no patient had a confirmed platelet count < 100,000/mm³. The incidence of minor bleeding events was comparable between the pooled placebo group (20.8%) and the pooled ISIS 678354 group (12.2%). No patient met any liver monitoring rules including increase in ALT or AST > $3 \times ULN$, or > $2 \times$ baseline (if baseline > $\times ULN$). The incidence of patients meeting any renal monitoring rules (decrease from Baseline in Estimated GFR [eGFR] > 25%, increase in serum creatinine > 0.3 mg/dL, urine albumin/creatinine ratio (UACR) > 250 mg/g, urine protein/creatinine ratio, (UPCR) > 500 mg/g) was comparable between the pooled placebo group (20.8%) and the pooled ISIS 678354 group (17.8%).

Treatment with AKCEA-APOCIII- L_{Rx} was not associated with any clinically significant changes in other laboratory parameters (including coagulation panel, and inflammatory marker, hsCRP), vital signs, or ECG parameters.

2.4. Rationale for Dose and Schedule of Administration

The starting dose and dosing regimens selected for this study are 50 mg or 80 mg every 4 weeks, which is supported by both the cumulative nonclinical data available to date and the Phase 1 and Phase 2 clinical data, as well as the medical need for maximal TG reduction for the highest proportion of FCS patients to get below the pancreatitis threshold of 750 mg/dL. The APPROACH trial demonstrated that volanesorsen mediated lowering of plasma apolipoprotein C-III levels in subjects with FCS effectively lowered plasma TGs below the threshold of 750 mg/dL that has been associated with TG-induced acute pancreatitis (Berglund et al. 2012; Brown et al. 2012; Scherer et al. 2014; Valdivielso et al. 2014; Brahm and Hegele 2015; Jacobson et al. 2015; Catapano et al. 2016; Witztum et al. 2019). Based on preclinical pharmacodynamic data with ISIS 678354, a dose of 80 mg will likely maintain TG levels below 750 mg/dL in a statistically significant number of subjects. This opportunity to achieve a TG level below 750 mg/dL will help maximize the opportunity to provide a potential impact on the risk of pancreatitis.

In nonclinical studies, ISIS 678354 demonstrated good safety profiles in rodents and monkeys. No nonclinical findings were considered to be related to the pharmacologic inhibition of apoC-III. In the monkey, the No Observed Adverse Effect Level (NOAEL) was defined by the cumulative clinical pathology results and histopathology data which provide an adequate clinical margin. The safety margins between the NOAEL in monkeys and the clinically relevant exposure are based on cumulative plasma AUC measurements (Yu et al. 2015) or mg/kg scaling (FDA 2005; Geary et al. 1997). The NOAEL in monkeys was determined to be 6 mg/kg/wk (1680 mg/month HED assuming 70 kg human body weight; AUC₀₋₄₈: 141 µg·h/mL). This NOAEL is approximately 21-fold above the current highest proposed clinical dose (80 mg/month: estimated AUC_{0-tau}: 6.7 µg·h/mL). Clinical safety data to date suggest that ISIS 678354 has been well-tolerated at dose levels up to 30 mg every week (equivalent to 120 mg every 4 weeks) in patients with high TGs with the most common AEs being local to the injection site and predominantly mild. A pooled analysis of safety for the Phase 1 and Phase 2 studies did not demonstrate any clear difference in safety or tolerability between the different doses tested (Phase 1: 10 mg, 30 mg, 60 mg, 90 mg, and 120 mg single dose, and 15 mg and 30 mg per week for 6 weeks (i.e., 60 mg and 120 mg cumulative monthly equivalents, respectively), and 60 mg every 4-weeks for 13 weeks. Phase 2: 10 mg and 50 mg every 4 weeks, 15 mg every 2 weeks, and 10 mg every week, all for at least 6 months and up to 1 year).

Analysis of the cohorts in which ISIS 678354 was studied at different dose levels demonstrates dose-dependent pharmacology with respect to pharmacodynamic effect on the target, apoC-III, with a clear difference in the TG-lowering effect between the different doses in the 10 mg to 120 mg per month equivalent dose range as compared to placebo. Considering the medical need for FCS patients with extremely high TG levels, often > 2000 mg/dL, achieving a maximal TG reduction over 70%, the level of reduction observed for volanesorsen at 300 mg every week dosing, is considered sufficient and necessary for ISIS 678354 to prevent the risk of acute

pancreatitis. Population PK/PD model-based simulations for a population of FCS patients predicted 70% reduction in TGs and 86% reduction in apo-CIII for 80 mg every 4-week dosing.

In addition to the nonclinical and clinical experience of ISIS 678354, the dose and schedule of administration is supported by the preclinical and clinical safety experience of several other 2'-MOE-modified, GalNAc₃-conjugated ASOs that have been safely administered SC in multiple clinical studies at doses up to 120 mg weekly for 12 weeks (ClinicalTrials.gov NCT03020745) and 20 mg weekly for up to 51 weeks (Tsimikas et al. 2020). The most advanced GalNAc₃-conjugated ASO (ISIS 681257; NVS TQJ230) of similar chemistry has entered into a large Cardiovascular Outcome Trial (HORIZON, NCT04023552) of 7600 subjects to be treated for a median of 4 years at a once-monthly dose of 80 mg every 4-week dosing. Cumulative safety and tolerability data from the platform as well as the preclinical and clinical experience for ISIS 678354 are supportive of this dose and dosing frequency (Crooke et al. 2018). Patients with FCS will require chronic treatment and therefore an every 4-week dosing regimen may provide advantages over weekly dosing in terms of convenience and compliance for patients.

2.5. Benefit-Risk Assessment

2.5.1. Overall Assessment of Benefit:Risk

The benefits of treatment of ISIS 678354 are currently unknown. Due to its mechanism of action, ISIS 678354 has the potential to be efficacious for the treatment of patients with FCS.

No specific risks have been identified with ISIS 678354 in the Phase 1 (678354-CS1) or Phase 2 (678354-CS2) studies. The conjugated nature of ISIS 678354 allows specific targeting of ASO to hepatocytes so, that for similar hepatocyte exposure, reduced exposure to both non-parenchymal liver cells and systemic exposure has the potential to lower apoC-III and TGs with an enhanced tolerability profile over the parent molecule, ISIS 304801. Consequently, platelet count decreases observed with the much higher doses of the unconjugated parent molecule are not anticipated to occur at the dose tested in this study.

Nevertheless, regular monitoring of platelet counts, liver chemistry, and renal function, and stopping rules will be included in the clinical study as described in Section 8.5 and Section 8.6.

Taking into account the measures implemented to minimize risk to patients participating in this study, the potential risks identified in association with ISIS 678354 are justified by the anticipated benefits that may be afforded to patients with FCS.

Detailed information concerning the benefit-risk assessment of ISIS 678354 can be found in the Investigator's Brochure.

2.5.2. Additional Risks During the COVID-19 Pandemic

Patients treated for hyperlipidemia should continue their regular regimen of diet and lifestyle measures and should also continue any approved pharmaceutical interventions for lipid lowering as no risks have been identified that would cause termination of treatment during the COVID-19 Pandemic (Iqbal et al. 2020) at this time.

There could be risk however, for patients who are participating in a clinical trial such as ISIS 678354. There may be risks to patients traveling to research sites. Sites should follow their

specific regional guidance (i.e., institutional, local, state, federal, country-level, as applicable) with regard to receiving patients for clinical trials. Visits should continue as long as it is deemed safe to do so. Provision will be available for patients to be treated or evaluated in their homes by a home healthcare professional. Additional mitigation steps and a study pause may be necessary as conditions warrant. If a study patient becomes infected with COVID-19 or develop COVID-19-related symptoms, the patient should notify the study staff/Investigator and notify their treating Physician that they are participating in a clinical trial with ISIS 678354.

3. EXPERIMENTAL PLAN

3.1. Study Design

This is a multi-center, randomized, double-blind, placebo-controlled study. Eligible patients will enter an approximately 4-week, but no more than 8-week, Screening Period that includes an at least 2-week Diet Stabilization/Run-In Period for patients not already on a stable diet, and an approximately 2-week Qualification Period. Following qualification, approximately 60 eligible patients will be randomized 1:1 to Cohort A (50 mg) or Cohort B (80 mg) and each cohort further randomized 2:1 to receive ISIS 678354 or placebo in a 53-week Treatment Period. Patients in Cohort A will receive 50 mg of ISIS 678354 once every 4 weeks or matching volume of placebo (0.5 mL) Weeks 1-49 of the Treatment Period. Patients in Cohort B will receive 80 mg ISIS 678354 once every 4 weeks or matching volume of placebo (0.8 mL) Weeks 1-49 of the Treatment Period. Randomization will be stratified by (1) prior history of pancreatitis (within 10 years prior to Screening) and (2) previous treatment with volanesorsen. Dietary counseling will commence at the start of the Diet Stabilization Period and will be reinforced at intervals throughout the Treatment and Follow-up Period. Following the Week 53 visit, eligible patients may elect to enroll in an open-label extension (OLE) study pending study approval by the institutional review board/independent ethics committee (IRB/IEC) and the appropriate regulatory authority. Patients not participating in the OLE will enter the 13-week Post-Treatment Evaluation Period. The primary endpoint for the study will be evaluated after the last patient has completed the Week 53/ET visit and will be based on the percent change in fasting TG from Baseline at the primary analysis time point (Month 6).

The patients, Investigators, study staff, and the Sponsor are to remain blinded to lipid data (central and local) starting after the first dose on Day 1 then throughout the remainder of the study.

3.2. Number of Study Centers

This study will be conducted at multiple centers worldwide.

3.3. Number of Patients

Approximately 60 patients are planned to be enrolled in this study.

3.4. Overall Study Duration and Follow-up

The study for an individual patient will generally consist of the following periods:

- An approximately 4-week, but no more than 8-week, Screening Period including a Diet Stabilization Period of at least 2 weeks and an approximately 2-week Qualification Period (patients on stable diet, for optimal control of TGs and disease management, known to the Investigator and followed at the site may go from Screening to Qualification without the Diet Run-In Period)
- A 53-week Treatment Period during which Study Drug will be administered as a once every 4-week SC injection (Week 1 through Week 49)
- A 13-week Post-Treatment Evaluation Period or transition to OLE Study

Please refer to the Schedule of Procedures in Appendix A.

3.4.1. Screening

A period of up to 8 weeks is given to complete the screening and baseline assessments outlined in the Schedule of Procedures in Appendix A.

3.4.2. Treatment Period

The Treatment Period is 53 weeks. Eligible patients will have assessments at specified intervals throughout the 53-week Treatment Period as outline in the Schedule of Procedures in Appendix A. During the Treatment Period, Study Drug is administered by SC injection once every 4 weeks.

3.4.3. Post-Treatment Period

The Post-Treatment Follow-up Period is 13 weeks with assessments as outline in the Schedule of Procedures in Appendix A.

Alternatively, following the Week 53 visit, eligible patients may elect to enroll in the OLE study pending study approval of this proposed study by the IRB/IEC and the appropriate regulatory authority.

3.5. End-of-Study

The End-of-Study is defined as last patient, last visit.

For individual patients, End-of-Study is defined as completion of their last study visit.

3.6. Data and Safety Monitoring Board or Independent Data Monitoring Committee

An independent Data and Safety Monitoring Board (DSMB) consisting of expertise in medical specialties relevant to the safety of ASO drugs (hematology, hepatology, and nephrology) will be assembled to review safety, tolerability and efficacy (as needed) data collected on ISIS 678354 during this study. Based on its ongoing assessment of the safety and tolerability of ISIS 678354, the DSMB will provide recommendations to the Sponsor for modifying, stopping or continuing the study as planned. Details on the safety assessments, frequency of review, meeting schedules

and controlled access to unblinded data are outlined in the DSMB Charter and Statistical Analysis Plan (SAP).

3.7. Allowances in the Circumstance of a Public Health Emergency

If an investigative site or the clinical trial patients associated with that site experience a public health emergency, such as a pandemic, then throughout that time the following changes to what is written elsewhere in this protocol are permissible, at the discretion of the Investigator, provided that all ICH, GCP, and regulatory requirements associated with the study are still upheld. These allowances may be implemented at any stage of the study: Screening Period, Treatment Period, and Post-Treatment Period. What is considered a public health emergency is based on circumstances and procedures at the site, and the judgment of the Investigator. The time at which a public health emergency has resolved to sufficient extent such that these allowances are no longer applicable is based on the judgment of the Investigator in consultation with the Medical Monitor.

- **Remote assessments and at-home visits**: Even when an investigative site remains open to clinical trial patients coming on site, social distancing strategies may result in some patients being unwilling or unable to attend protocol-specific clinic visits. For such reasons, scheduled clinic visits may be replaced by remote assessments (via video conference or telephone call) or at-home visits or a combination, provided that these are properly documented. This may be accomplished by at-home visits by Study Center staff or home healthcare providers, with incorporation of videoconference or telephone assessments by Study Center staff or designee.
- **Randomization**: When a patient is found to be eligible for the study, the decision regarding if and when the patient will be randomized is based on the judgment of the Investigator in consultation with the Medical Monitor. Randomization may be delayed by up to 1 month without rescreening.
- **Safety assessments**: Every effort should be made to continue performing safety assessments on schedule. This may require remote assessments (e.g., for adverse events and concomitant medications) by Study Center staff, and it may require at home visits (e.g., for blood draws, urine samples, physical examination, vital signs) by Study Center staff or home healthcare providers. Which safety assessments are considered critical, for example to support a decision on whether to administer the next scheduled dose of Study Drug to a patient, is to be determined on a case-by case basis by the Investigator in consultation with the Medical Monitor.
- **Reporting of protocol deviations**: All protocol deviations that are caused by a public health emergency should be documented as such; for example, include in the description of the protocol deviation that it is related to COVID-19. The impact such protocol deviations had on the study is to be summarized in the clinical study report. This summary is considered sufficient notification of the EC / IRB for minor protocol deviations that were caused by a public health emergency.
- Laboratory assessments associated with primary or secondary endpoints: Every effort should be made to perform the assessments on schedule.

- **To support Study Drug administration at home**, delivery of Study Drug to the patient may be undertaken at the discretion of the Investigator, based on local and regional regulations for transporting investigational product.
- Immunization of patients with a vaccine for COVID-19, or antiviral treatments under an emergency use authorization for COVID-19, outside of a clinical trial, may occur while patients are on study, however it is preferable that a separation of at least 7 days occurs between administration of the vaccine or antiviral and administration of Study Drug. Adjustment of the schedule for monthly administration of Study Drug may be considered in order to achieve this separation. In addition, Study Drug should not be injected into the same anatomical location as the vaccine for COVID-19.

4. **PATIENT ENROLLMENT**

4.1. Screening

Before patients may be enrolled into the study, the Sponsor or designee requires a copy of the Study Center's written IEC/IRB approval of the protocol, informed consent form, and all other patient directed information and/or recruitment material.

Patients or their legally acceptable representatives must sign the consent form before any screening tests or assessments are performed. At the time of consent, the patient will be considered enrolled into the study and will be assigned a unique screening number before any study procedures, including screening procedures, are performed. The screening number and patient identification number must remain constant throughout the entire trial. Patients may be re-screened 1 time in order to determine eligibility. In the event the patient is re-consented and re-screened the patient must be given a new screening number. Screening numbers and patient identification numbers, once assigned, will not be re-used.

4.2. Randomization

Patients will be randomized after all screening assessments have been completed and after the Investigator has verified that they are eligible per criteria in Section 5.1 and Section 5.2. No patient may begin treatment prior to randomization and assignment of a unique patient identification number.

Using an Interactive Response Technology (IRT) system, eligible patients will be randomized 1:1 to Cohort A or Cohort B and each cohort further randomized 2:1 to receive ISIS 678354 or placebo. Patients will be stratified for:

- Prior history of pancreatitis within 10 years prior to Screening* vs. no history of pancreatitis or no history within 10 years prior to Screening
- Previous treatment with volanesorsen (Yes vs. No)
- * History of pancreatitis is defined as a recorded diagnosis of acute pancreatitis or hospitalization or ER visit for severe abdominal pain consistent with acute pancreatitis and for which no alternate diagnosis was made.

The randomization lists will be prepared by an independent external vendor.

4.3. Replacement of Patients

Patients who withdraw from the study will not be replaced.

4.4. Unblinding of Treatment Assignment

The Sponsor and all patients, monitors, and Study Center personnel related to the study will be blinded throughout the study until all patients have completed the study and the database has been locked. Representatives from the Sponsor may be unblinded after the last patient has completed the end of the treatment period (Week 53/ET) as described in the Unblinding Plan. Those Sponsor representatives will no longer be involved in the conduct of the study after they have been unblinded.

However, if a patient has suffered an SAE (as defined in Section 9.3.3), and/or when knowledge of the treatment assignment will impact the clinical management of the patient, the Investigator will have the ability to unblind the treatment assignment for that patient using the IRT.

The Sponsor or designee will be informed of the unblinding of a subject within 24 hours. An unblinded randomization schema will be maintained securely at the Sponsor's designated vendor. In addition, all suspected unexpected serious adverse reaction (SUSARs) will be unblinded by the Sponsor or designee for the purpose of unblinded regulatory reporting (see Section 9.2).

Every reasonable attempt should be made to complete the early termination study procedures and observations (see Appendix A) prior to unblinding, as knowledge of the treatment arm could influence subject assessment.

5. **PATIENT ELIGIBILITY**

To be eligible to participate in this study candidates must meet the following eligibility criteria within 8 weeks of Study Day 1 or at the time point specified in the individual eligibility criterion listed.

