8.8. Discontinuation of Study Drug

A patient must permanently discontinue Study Drug treatment for any of the following:

- The patient becomes pregnant. Report the pregnancy according to instructions in Section 9.5.4
- The patient withdraws consent
- The patient experiences an AE that necessitates permanent discontinuation of Study Drug
- The patient develops laboratory test abnormalities that meet any of the stopping rules listed in Section 8.6.1 to Section 8.6.3
- The patient experiences an AE that necessitates unblinding of the Investigator or Sponsor to the patient's treatment assignment

The reason for discontinuation of Study Drug must be recorded in the eCRF and source documentation.

8.8.1. Follow-up Visits for Early Termination from Treatment Period or Post-Treatment Follow-up Period

Any patient who discontinues early from the Treatment Period should be strongly encouraged to attend applicable landmark visits at Weeks 23, 25, 27 and Weeks 51 and 53 (calculated based on the time elapsed since Day 1) to collect fasting lipid panels and conduct safety assessments in accordance with Appendix A. Any patient who discontinues early from the Post-Treatment Follow-up Period should be strongly encouraged to complete follow-up study visits, procedures and observations in accordance with Appendix A.

Any patient who discontinues early from the Treatment Period or from Post-Treatment Follow-up Period should be followed as per the platelet monitoring rules shown in Table 2, Section 8.6.3 for the first 6 weeks Post-End of Treatment Period and then at 8 and 13 weeks Post-End of Treatment Period (as per visit schedule).

If a patient discontinues early from the Treatment Period and declines or is unable to participate in the above, an ET visit (Week 53 visit assessments) should be performed at the time of withdrawal, and ideally within 2 weeks from the last dose of Study Drug, and patients should start the 13-week Post-Treatment Follow-up Period to collect the study assessments in accordance with the Schedule of Procedures in Appendix A.

If the patient discontinues early from the Post-Treatment Follow-up Period and declines or is unable to participate in the above, a final visit (assessments from Week 13 of the Post-Treatment Follow-up Period) should be performed at the time of withdrawal.

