9.2. Regulatory Requirements

The Sponsor or designee is responsible for regulatory submissions and reporting to the Investigators of serious adverse events (SAEs) including SUSARs per the International Conference on Harmonization (ICH) guidelines E2A and ICH GCP. Country-specific regulatory requirements will be followed in accordance with local country regulations and guidelines.

Institutional Review Boards/Independent Ethics Committees will be notified of any SAE according to applicable regulations. The DSMB will be notified of any SAE as specified in the DSMB charter.

In addition to the Investigator's assessment of relatedness, the Sponsor or designee will evaluate the available information and perform an independent assessment of all reported SAEs and determine if there is a reasonable possibility that the Study Drug (ISIS 678354 or placebo) is causally related to a reported SAE.

The Sponsor or designee will evaluate the available information for all reported SAEs and decide if there is a reasonable possibility that the Study Drug (ISIS 678354 or placebo) caused the SAE and, therefore, meets the definition of a SUSAR.

Appropriate personnel at the Sponsor or designee will unblind SUSARs for the purpose of regulatory reporting. The Sponsor or designee will submit SUSARs to Regulatory Agencies in blinded or unblinded fashion according to local law. The Sponsor or designee will submit SUSARs to Investigators in a blinded fashion.

The following table identifies the SAEs that the Sponsor or designee will not report on an individual basis in an expedited manner because they are anticipated to occur in the study population independent of the Study Drug (ISIS 678354 or placebo) exposure. The Investigator still has the responsibility to report all SAEs to the Sponsor as described in Section 9.4.1 to Section 9.4.3.5.

Table 4:Expected Event for the Protocol Defined Population by Preferred Term and
Expected Incidence

Preferred Term	Expected Incidence in the Protocol Defined Population (Gaudet et al. 2010; 2013)
Pancreatitis associated events including the PTSs of hereditary pancreatitis, pancreatitis, pancreatitis acute, pancreatitis chronic, pancreatitis necrotizing, pancreatitis relapsing	0.2–0.35 events per patient year

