9.3.3. Serious Adverse Event

A serious AE is any AE that in the view of either the Investigator or Sponsor, meets any of the following criteria:

- Results in death
- Is life threatening: that is, poses an immediate risk of death at the time of the event

An AE or suspected adverse reaction is considered "life-threatening" if, in the view of either the Investigator or Sponsor, its occurrence places the patient at immediate risk of death. It does not include an AE or suspected AE that, had it occurred in a more severe form, might have caused death

- Requires inpatient hospitalization or prolongation of existing hospitalization
- Results in a persistent or significant incapacity or substantial disruption of the ability to conduct normal life functions
- Results in a congenital anomaly or birth defect in the offspring of the patient (whether the patient is male or female)
- Important medical events that may not result in death, are not life-threatening, or do not require hospitalization may also be considered serious when, based upon appropriate medical judgment, they may jeopardize the patient and may require medical or surgical intervention to prevent one of the outcomes listed in this definition. Examples of such medical events include allergic bronchospasm requiring intensive treatment in an emergency room or at home, blood dyscrasias or convulsions that do not result in inpatient hospitalization, the development of drug dependency or drug abuse, or spontaneous abortion/miscarriage.

The terms "severe" and "serious" are not synonymous. Severity refers to the intensity of an AE (e.g., rated as mild, moderate, or severe, or according to National Cancer Institute Common Terminology Criteria for Adverse Events [NCI CTCAE]; OR Toxicity Grading Scale for Healthy Adult and Adolescent Volunteers Enrolled in Preventive Vaccine Clinical Trials; the event itself may be of relatively minor medical significance (such as severe headache without any further findings).

Severity and seriousness need to be independently assessed for each AE recorded on the eCRF.

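### Section 4.4 lets an investigator break the blind after any SAE without need, so a pancreatitis admission, itself a secondary endpoint event, can open the code

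*Combined protocol and SAP*

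**What the plan says.** Section 4.4 sets blinding until database lock as the default and then gives an exception. The condition is "if a patient has suffered an SAE (as defined in Section 9.3.3), and/or when knowledge of the treatment assignment will impact the clinical management", and when it is met "the Investigator will have the ability to unblind the treatment assignment for that patient using the IRT". The control stated is after the fact: "The Sponsor or designee will be informed of the unblinding of a subject within 24 hours". The section also asks sites to try to complete early termination procedures before unblinding, "as knowledge of the treatment arm could influence subject assessment".

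Section 9.3.3 includes among the SAE criteria "Requires inpatient hospitalization or prolongation of existing hospitalization". Table 4 in Section 9.2 lists SAEs anticipated in this population regardless of Study Drug. Its one row begins "Pancreatitis associated events including the PTSs of hereditary pancreatitis" and gives an expected incidence of "0.2–0.35 events per patient year".

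Section 8.8 lists reasons for permanent discontinuation of Study Drug. One is worded by need: "The patient experiences an AE that necessitates unblinding of the Investigator or Sponsor" to the patient's assignment.

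Adjudicated acute pancreatitis rate accounts for 6 of the 17 secondary endpoints in Section 1.2.2, and for positions 13 to 16 and 25 to 26 of the 28 ordered tests in SAP Section 4.9.1.3. SAP Section 4.9.3.5 models event counts and keeps adjudicated events that follow intercurrent events.

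**The concern.** The SAE limb adds code-breaks that serve no management purpose, and it catches an efficacy outcome. After a first admission the site may learn the arm and then go on deciding how later abdominal pain in that patient is worked up and whether it is reported as suspected pancreatitis. The adjudication committee is blinded, but it rules on events that reach it. If an unblinded site investigates or reports differently by arm, the recurrent-event count can be biased before adjudication begins. The exploratory ER-visit and hospitalisation rates are open in the same way. With few events in the trial, a small number of differentially handled ones could move a rate ratio.

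**Working it through.** The plan gives no expected number of code-breaks or pancreatitis events, so there is no figure of its own to reproduce. The point rests on the text; the arithmetic only gives scale.

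**1. What the condition permits**

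| SAE? | Assignment needed for management? | Code-break under 4.4? | Discontinuation item in 8.8? |
|---|---|---|---|
| Yes | Yes | Yes | Applies if the AE makes unblinding necessary |
| No | Yes | Yes | Applies if the need comes from an AE |
| Yes | No | Yes | Not clearly covered: nothing made unblinding necessary |
| No | No | No | Not applicable |

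The third row is the problem. Section 4.4 does not narrow it by type of SAE or relatedness, and asks for no prior consultation.

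**2. Overlap with the endpoint.** A pancreatitis admission meets the hospitalisation criterion in Section 9.3.3. It also goes to adjudication under Section 9.4.3.7. One event can therefore be both an endpoint count and a ground for unblinding.

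**3. After the code-break.** SAP Section 4.9.3.5 counts later adjudicated events whether or not Study Drug was stopped, and accepts categories down to possible pancreatitis. Protocol Section 6.3.2 leaves imaging to be considered when lipase or amylase is below 3 × ULN. Work-up of later pain therefore has a discretionary part. The estimand tables in SAP Section 4.9.2 name treatment discontinuation and disallowed therapy as intercurrent events, not unblinding, and no planned analysis sets aside data collected after a code-break.

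**4. Scale.** Inputs: rate r = 0.2 to 0.35 per patient-year (Table 4); N = 60 (Section 3.3). Assumptions: one year of follow-up each, the Table 4 rate in every patient, independent Poisson events.

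- All events, N × r: 60 × 0.2 = 12; 60 × 0.35 = 21.
- Patients with at least one event, N × (1 − e^(−r)): 60 × 0.1813 = 10.9; 60 × 0.2953 = 17.7.
- Events beyond a patient's first, the difference: 12 − 10.9 = 1.1; 21 − 17.7 = 3.3.
- In the 20 planned placebo patients alone: 20 × 0.2 = 4 and 20 × 0.35 = 7 events in all, of which 20 × (0.2 − 0.1813) = 0.4 and 20 × (0.35 − 0.2953) = 1.1 would be repeats.

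Using 364 days in place of a full year changes 12 and 21 to 11.96 and 20.93.

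The 12 to 21 is an upper figure for pancreatitis-triggered code-break opportunities: two-thirds of patients receive active drug, not every event need be serious, and a patient can be unblinded only once. The 1 to 3 is closer to the events at risk. It would rise with clustering of attacks within patients and fall with a treatment effect. A code-break after an unrelated SAE could also expose a patient's first attack, which the 1 to 3 does not count.

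**The case against.** The case on the other side is substantial. Section 4.4 gives an ability, not an instruction, and recognises this bias by asking for assessments before unblinding. The index event precedes the code-break it triggers and is adjudicated blind. All SAEs must be reported within 24 hours whatever their relationship to drug (Section 9.4.1), so a later admission may not be withheld. Patients carry a card asking the treating physician for enzyme tests, so work-up can begin outside the site. ER visits and hospitalisations are asked about at each visit. The Unblinding Plan, adjudication charter and IRT instructions are not available here and may restrict code-breaks further.

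All of this reduces the exposure. It does not close it, because later pain that does not lead to admission still depends on site judgement, and completing procedures beforehand protects only data already collected. Section 4.4 cites the Unblinding Plan for sponsor staff after the last Week 53 visit, not as a limit on investigators.

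Four stronger readings are tempting, and the documents do not support them:

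- A reader might infer a threat to the trial's principal result. The primary endpoint is fasting triglyceride change, a laboratory measure; pancreatitis is secondary.
- A reader might infer that the lipid blind fails. A code-break reveals the arm but no lipid values. Section 3.1 and SAP Section 4.1.1 keep those masked, with only the LDL-C alert excepted.
- A reader might take 12 to 21 as the number of events open to bias. That figure includes first attacks and applies an untreated rate to every arm.
- A reader might add the symptom diary. Patients enter it themselves, and nothing in Section 4.4 says the patient is told the assignment.

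**Conclusion.** The point holds in limited form. On its wording, Section 4.4 permits unblinding after any SAE without need, and a secondary endpoint event can be the SAE that permits it. What is exposed is the work-up and reporting of later pancreatitis, and ER and hospitalisation data, in patients whose code was broken. The scale is about 1 to 3 repeat events out of about 12 to 21, under the Table 4 rate, 60 patient-years and a Poisson model. Table 4 also includes chronic and hereditary pancreatitis terms, so it is only a rough guide to adjudicated acute events. The documents do not show that any such code-break took place, and they do not establish the direction of any bias. The change is worth making because the route is avoidable and the fix is small. Separately, Sections 4.4 and 8.8 do not fit together for a patient unblinded on the SAE limb alone and must be reconciled.

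**What to change.** Delete the SAE limb and 'and/or' from Section 4.4, so that investigator unblinding rests on the need-based condition already there. Leave sponsor unblinding of SUSARs unchanged. The sponsor should also reconcile Section 4.4 with the discontinuation item in Section 8.8 so that the status of every unblinded patient is clear. The cost is one protocol sentence, a cross-check of Section 8.8 and matching IRT instructions; need-based emergency access is unaffected.

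The results summary at the front of the document says the study ended in October 2023. If conduct is complete, list every code-break by arm, date and reason. If there were none, the listing settles the matter. If there were some, repeat the pancreatitis models with follow-up censored at unblinding, labelled post hoc. Censoring soon after an event is informative, so that analysis is supportive only. It needs one listing and a rerun of existing models with revised counts and offsets.
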